5.5.1 Study PLX121-01: Preliminary Results

The study described in this protocol, PLX121-01, is a 2-part Phase 1b/2a trial to assess the safety, PK, PD, and preliminary efficacy of PLX9486 as a single agent and when used in

combination with PLX3397 or sunitinib in patients with advanced solid tumors and in patients with locally advanced, unresectable, or metastatic GIST who have previously been treated with KIT-directed TKI. The phase 1 portion of the study (Part 1) has been completed.

5.5.1.1 Study PLX121-01 Part 1

Twenty-four patients were enrolled among 5 dose-escalation cohorts ranging from 250 mg/day to 1000 mg/day (Table 10). One DLT was observed in the 1000 mg QD cohort (Grade 3 anemia). Table 11 summarizes the Day 1 and Day 15 (steady state) PK results for these cohorts. The data show a modest increase in exposure at steady state between the 250 mg/day dose ($AUC_{0-24}=18,500 \text{ ng}\cdot\text{hr}/\text{mL}$) and the 1000 mg/day dose ($AUC_{0-24}=21,500 \text{ ng}\cdot\text{hr}/\text{mL}$ [QD] and $24,400 \text{ ng}\cdot\text{hr}/\text{mL}$ [BID]). The difference in exposure between the 1000 mg QD dose and the 500 mg BID dose is not statistically significant. Because AUC_{0-24} at 1000 mg QD reaches the target exposure range (AUC_{0-24} of 19,000 to 36,000 $\text{ng}\cdot\text{hr}/\text{mL}$) and because a further increase in dose is not expected to significantly improve AUC, 1000 mg QD was selected as the RP2D for single-agent PLX9486. A single DLT (Grade 3 anemia; 1000 mg QD) was reported among the 24 patients.

Table 10: Study PLX121-01 Part 1 Patient Enrollment and DLT Summary

Part 1 Cohort	PLX9486 Dose Level	Number Enrolled	Number of DLTs (Adverse Events)
1	250 mg QD	3	0
2	350 mg QD	4	0
3	500 mg QD	3	0
4	1000 mg QD	7	1 ^a
5	500 mg BID	7	0

BID = twice daily; DLT = dose-limiting toxicity; QD = once daily

^a DLT: Grade 3 anemia.

Table 11: Study PLX121-01 Part 1 (Dose Escalation) Pharmacokinetic Profile of Single-agent PLX9486 in Patients with Advanced Solid Tumors

Dose		C1D1		C1D15 (Steady State)			Accumulation Ratio
		C _{max} (ng/mL)	AUC _{0-τ} ^a (ng·hr/mL)	C _{max} (ng/mL)	C _{min} (ng/mL)	AUC ₀₋₂₄ (ng·hr/mL)	
250 mg QD (N = 3)	GeoMean	499	9240	869	716	18500	2.0
	CV%	6.92	8.7	38.4	42.5	43.7	
350 mg QD (N = 4)	GeoMean	348	7200	1010	789	21300	3.0
	CV%	15.0	20.7	27.5	27.9	27.7	
500 mg QD (N = 3)	GeoMean	326	5250	714	462	15400	2.9
	CV%	28.5	37.3	64.9	119	65.8	
1000 mg QD (N = 7)	GeoMean	558	11000	1060	722	21500	2.0

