9.2.1.2 Part 2: Extension Cohorts

[REDACTED]

Part 2b. Cohorts of patients will be enrolled using the standard “3+3” design. The PLX9486 dose escalation may follow the pattern established in Part 1, starting at $\leq 50\%$ of the MTD/RP2D established in Part 1. In the absence of Grade ≥ 2 toxicity that is considered “possibly” or “probably” related to the study agent and in conjunction with review of the pharmacokinetic data, dose escalation in Part 2b is planned to occur as indicated in [Table 17](#).

Table 17: PLX9486 and PLX3397 Administration in Part 2b: Initial and Potential Dose-escalation Cohorts

Cohort Number	PLX9486 Dose Level (mg/day) ^a	PLX3397 Dose Level (mg/day)
1	Approximately 50% of Part 1 RP2D	600 (200 mg in AM and 400 mg in PM)
2	Approximately 100% of Part 1 RP2D	600 (200 mg in AM and 400 mg in PM)
3	100% of Part 1 RP2D	400 mg QD (Cycles 1 and 2)
		600 mg QD (Cycle 3 +) ^b
4 +	TBD ^c	TBD ^c

RP2D = recommended phase 2 dose; TBD = to be determined

^a PLX9486 administered once-daily (QD) or for higher total daily doses, as split doses (e.g., twice-daily [BID]).

^b At the discretion of the investigator and in the absence of clinically significant drug-related toxicity ([Section 9.3](#)) during Cycles 1 and 2.

^c Based on a review of the data by the Study Committee.

Dose escalation will continue unless there are DLTs in ≥ 2 of 6 patients in one cohort within the first 28 days of continuous dosing.

[figure not shown]
Further dose escalation and reduction in smaller increments may be undertaken at any time based upon emerging safety, PK, and PD data. Dose adjustments may also include increasing the number of patients at a given dose level as a result of the review of safety and PK data by the Sponsor and investigators. In addition, alternative dosing schedules may be explored, such as continuous dosing followed by a rest period, staggered dosing of the agents, etc., depending on the safety, PK, or PD-generated data, as well as data from other ongoing PLX3397 studies.

If a DLT is observed in one patient at a given cohort, an additional 3 patients will be enrolled into the cohort. If DLT is observed in ≥ 2 of at least 6 patients (i.e., $\geq 33\%$) at a dose level, then a lower dose level of PLX9486 may be introduced to the combination regimen. If no DLT is

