9.2.4 Dose De-escalation for PLX9486 combinations

Combination with PLX3397: If ≥ 2 of the first 6 patients who receive the first dose level in Part 2b experience a protocol-defined DLT, the administration of PLX9486 and PLX3397 will be considered too toxic and dosing will be reconfigured.

PLX3397 dose de-escalation will be in decrements of 200 mg per day. Examples of these dose reductions are provided in [Table 21](#).

Table 21: PLX3397 Examples of Dose Reductions for the 600 mg Daily Dosing Cohorts

Dose Level	When
600 mg	Starting dose
400 mg	1 st dose reduction
200 mg	2 nd dose reduction
Off study	3 rd dose reduction required

Combination with sunitinib: If ≥ 2 of the first 6 patients who receive the first dose level in Part 2e experience a protocol-defined DLT, the administration of PLX9486 and sunitinib will be considered too toxic and dosing will be reconfigured as follows:

- Hold sunitinib for \geq Grade 3 drug related AEs
 - First occurrence:
 - Hold drug until AE \leq Grade 1 for non-hematologic events or AE \leq Grade 2 for hematologic events. Resume at same dose level if at 37.5 mg dose.
 - For Grade 3 treatment-related AE, dose reduce to 25 mg if at 37.5 mg or resume at reduced dose of 25 mg.

- For Grade 4 treatment-related AE, if at 25 mg dose level, hold sunitinib until AE \leq Grade 1 for non-hematologic events or AE \leq Grade 2 for hematologic events, then resume at 25 mg dose level or discontinue sunitinib
- Second occurrence:
 - Hold sunitinib until AE \leq Grade 1 for non-hematologic events or AE \leq Grade 2 for hematologic events. If at 37.5 mg, dose reduce to 25 mg, and if at 25 mg, discontinue sunitinib

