9.4 Dose Modification Guidelines and Stopping Rules

Toxicities that occur outside the DLT window will be taken into consideration when determining the RP2D. Reduction/interruption of dosing for AEs may take place at any time. [Table 22](#) summarizes the guidelines for dosage modification (including stopping rules) for PLX9486-related toxicities as well as guidelines for their management. Dose reductions for PLX9486 should occur in decrements of 200 mg per day and for PLX3397 should occur in decrements of 200 mg/day, depending on the toxicity grade, as noted in [Table 21](#). [Table 23](#) summarizes the guidelines for dosage modification (including stopping rules) for PLX3397-related toxicities (excluding liver function abnormalities) and guidelines for their management. [Table 24](#) summarizes the guidelines for PLX3397 dosage modifications (including stopping rules) for liver function abnormalities, and [Table 25](#) provides additional liver evaluations for the management of liver function abnormalities.

Dose reductions of one or both study drugs will be made based on the known toxicity of PLX3397 and on the specific toxicity of PLX9486, and will be made only after decision by the Sponsor's medical monitor in discussion with the investigator(s). The dose modification guidelines in [Table 22](#) are applicable to all parts of the study. Dose modifications of sunitinib should follow the USPI, as well as the guidance below.

If a stable combination dose of PLX9486 and PLX3397 is unattainable, dosing will be halted and a new dose configuration with a lower dose of PLX3397 (e.g., 600 mg PLX3397 and 150 mg PLX 9486) will be developed. For the combination parts of the study (Part 2b and [redacted]), if one study drug needs to be temporarily discontinued due to an adverse event, then both drugs need to be discontinued until the adverse event resolves per the dose modification guidelines. If one study drug needs to be permanently discontinued, then both study drugs must be permanently discontinued and the patient taken off-study.

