10.3 Treatment Group Assignments

This is an open-label, sequential dose-escalation study with extension cohorts. The initial dose level of PLX9486 will be 250 mg/day. Thereafter, dose-escalation groups will occur as described in [Section 9.2.1](#). Extension cohorts will be enrolled in parallel at the RP2D according to inclusion and exclusion criteria ([Section 8.1](#) and [Section 8.2](#)). The initial dose of PLX3397 will be 600 mg/day administered BID. Thereafter, dose escalation groups will occur as described in [Section 9.2.1.2](#). For the combination cohort with sunitinib the initial sunitinib dose will be 25 mg/day. Further details may be found in [Section 9.2.1.2](#).

10.4 Withdrawal of Patients from Drug Treatment or from the Study and Patient Replacement

The Plexxikon Medical Monitor will monitor safety data throughout the course of the study. The Medical Monitor will review SAEs within timeframes mandated by company procedures and will review trends, laboratory data, and AEs at periodic intervals and provide for interim safety analyses if appropriate.

The reasons a patient may discontinue or be withdrawn from the study include, but are not limited to, adverse event, clinically significant disease progression, patient request, investigator decision, protocol violation, patient noncompliance, and study termination by the Sponsor or institutional review board (IRB)/independent ethics committee (IEC). When a patient discontinues or is withdrawn, the investigator will notify the Sponsor and should perform the procedures indicated in the End of Study column in the Schedule of Events within 30 days after discontinuation of study drug and before initiation of any new anti-cancer therapy. Follow-up information will be obtained for patients who discontinue their participation in or are withdrawn from the study.

Patients withdrawn from the study for reasons other than toxicity or clinically significant disease progression (e.g., protocol violation or noncompliance) may be replaced at the discretion of the medical monitor and the investigator. Study drug administration may be discontinued due to an adverse event or at the discretion of the investigator.

The consequence of withdrawal of consent by a patient will be that no new information will be collected from that patient and added to the existing data or any database. However, every effort will be made to follow all patients for safety.

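### Section 9.4 calls for a lower PLX3397 dose when the PLX9486 + PLX3397 combination fails, but its example keeps PLX3397 at 600 mg/day and lowers only PLX9486

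*Protocol*

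**What the plan says.** Section 9.4 provides for the case in which no stable dose of the PLX9486 + PLX3397 combination can be reached. Dosing is halted and the follow-on is "a new dose configuration with a lower dose of PLX3397 (e.g., 600 mg PLX3397 and 150 mg PLX 9486").

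The PLX3397 doses elsewhere in the protocol are:

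- Section 10.3: "The initial dose of PLX3397 will be 600 mg/day administered BID".
- Table 17 (Section 9.2.1.2), Part 2b Cohorts 1 and 2: "600 (200 mg in AM and 400 mg in PM").
- Table 17, Cohort 3: "400 mg QD (Cycles 1 and 2"), then 600 mg QD from Cycle 3 at the investigator's discretion. Cohort 4 and beyond are still to be determined.
- Section 9.2.4: "PLX3397 dose de-escalation will be in decrements of 200 mg per day". Table 21 applies this as 600, 400, 200 mg, then off study.

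Two other places deal with a combination dose level that proves too toxic. Section 9.2.1.2 says that with DLTs in 2 or more of at least 6 patients, "then a lower dose level of PLX9486 may be introduced to the combination regimen". Section 9.2.4 says of the first Part 2b level that "the administration of PLX9486 and PLX3397 will be considered too toxic and dosing will be reconfigured", without naming a drug.

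**The concern.** The operative words and the example that should illustrate them point to different drugs. The words reduce PLX3397. The example leaves PLX3397 at its full starting dose and makes a large cut in PLX9486.

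The sentence describes what happens after a combination has failed, and PLX3397 is the partner with the serious documented liver risk: Section 5.6.1 reports severe cholestasis, one transplant and one fatal case with ongoing cholestatic injury. Someone who took the figures at face value would keep the PLX3397 dose unchanged where the words call for reducing it. The synopsis says patients were still being treated in Part 2b at the time of this amendment, so the section was in use.

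**Working it through.** No statistical figure is involved. The check compares the example doses with the protocol's own dose levels.

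**Inputs**

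- Example (Section 9.4): PLX3397 600 mg, PLX9486 150 mg.
- PLX3397 levels (Table 17): 600 mg/day in Cohorts 1 and 2; 400 mg in Cohort 3 Cycles 1 and 2; 600 mg in Cohort 3 from Cycle 3.
- PLX3397 ladder (Section 9.2.4, Table 21): steps of 200 mg/day from 600 mg.
- PLX9486 levels: Section 5.5.1.1 states that "1000 mg QD was selected as the RP2D for single-agent PLX9486". Table 17 uses about 50% of this in Cohort 1 and 100% (approximately so in Cohort 2) in Cohorts 2 and 3. Section 5.5.1.2 confirms that 500 mg was the 50% dose actually given.

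**Formulas.** Change = example dose − reference dose. Percentage change = change ÷ reference dose.

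**PLX3397, the drug the words say is lowered**

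- Against Cohorts 1 and 2: 600 − 600 = 0 mg.
- Against Cohort 3 from Cycle 3: 600 − 600 = 0 mg.
- Against Cohort 3 in Cycles 1 and 2: 600 − 400 = +200 mg.
- Against the first row of Table 21: 600 − 600 = 0 mg, that is, no step down.

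No comparison gives a reduction. For Cohort 3 during the DLT window, which is Cycle 1 (Section 9.3), the example would be an increase.

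**PLX9486, the drug the example does lower**

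- From 500 mg: 150 − 500 = −350 mg; −350 ÷ 500 = −70%.
- From 1000 mg: 150 − 1000 = −850 mg; −850 ÷ 1000 = −85%.

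**What a lower PLX3397 dose would be on the protocol's own ladder**

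- From 600 mg: 600 − 200 = 400 mg; −200 ÷ 600 = −33%.
- From 400 mg: 400 − 200 = 200 mg; −200 ÷ 400 = −50%.

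**The case against.** Nobody can argue that 600 mg is below 600 mg. The case on the other side is that the slip has little force, and most of that case stands.

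- **Which drug is reduced is governed elsewhere.** A reader might infer that the protocol leaves this open. It does not. Just before the disputed sentence, Section 9.4 says that one or both drugs are reduced according to their toxicities, and only after the medical monitor has decided in discussion with the investigators. Section 9.2.1.2 allows a lower PLX9486 level after a cohort-level DLT finding. Tables 21, 23 and 24 give PLX3397 steps for individual patients, with liver abnormalities covered in Table 24.
- **The sentence is not a dosing order.** Dosing is halted and a configuration is still to be worked out. The figures are an example, and Section 9.4 describes its parameters as guidance that does not replace clinical judgment. No site would dose a patient from this parenthesis alone.
- **A lower PLX3397 regimen already exists**, namely the 400 mg start in Cohort 3.
- **There is no sign that the fallback was used.** Section 5.5.1.2 reports no Part 2b DLTs as of December 2017. The synopsis reports one DLT in all up to 26 April 2019, on single-agent PLX9486 in Part 1.

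A reader might also infer that the parallel sunitinib sentence in Section 9.4 has the same fault, because its 25 mg example equals the dose of Part 2e Cohorts 1 and 2. The documents do not support that. Table 18 has a 37.5 mg cohort, and 25 mg is a true reduction from it: (25 − 37.5) ÷ 37.5 = −33%. An example need not fit every cohort, and Section 9.2.4 covers patients already at 25 mg by holding and resuming, or by stopping. The PLX3397 example differs because 600 mg is below no named level.

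These points limit the consequence. They do not make the example agree with its rule.

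**Conclusion.** The point holds as a low-severity internal inconsistency, wrong as written. The example lowers PLX3397 by 0 mg against every 600 mg level, exceeds the Cohort 3 entry dose by 200 mg, and cuts only PLX9486, by 70% or 85%. No escalation rule, DLT definition, sample size, endpoint or analysis depends on it, and the practical risk is small because the medical monitor and investigators set the actual dose.

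This rests on two assumptions. First, the redacted parts and the undetermined Cohort 4 and beyond contain no PLX3397 level above 600 mg/day; the visible text names none. Second, the PLX9486 reference doses are 500 and 1000 mg, as reported in Section 5.5.1. The documents do not show whether the words or the example reflect the sponsor's intention.

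**What to change.** Keep the operative words in Section 9.4 and replace the PLX3397 figure with a dose below the failed level on the 200 mg/day ladder of Table 21: 400 mg, or 200 mg if 400 mg was the dose that failed. If the sponsor meant PLX9486 to be reduced, change the words so that they name PLX9486, in line with Section 9.2.1.2. The sunitinib sentence needs no change.

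The cost is one corrected sentence, which can go into the next amendment. It has no effect on sample size, visit schedule or data already collected.

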If a stable combination dose of PLX9486 and sunitinib is unattainable, dosing will be halted and a new dose configuration with a lower dose of sunitinib (e.g., 25 mg sunitinib and 150 mg PLX 9486) will be developed. For the combination parts of the study (Part 2e and [redacted]), if one study drug needs to be temporarily discontinued due to an adverse event, then both drugs need to be discontinued until the adverse event resolves per the dose modification guidelines. If one study drug needs to be permanently discontinued, then both study drugs must be permanently discontinued and the patient taken off-study.

These parameters are only a guide and are not intended to supersede the clinical judgment of the treating physician. The dose modification/reduction guidelines are for clinically significant toxicities that are at least possibly related to study drug administration. Definitions of "clinically significant" and "related" will be made based on the judgment of the investigator and the case discussed with the Medical Monitor as needed. All adjustments should be made in consultation with the Medical Monitor. Dosing interruptions longer than 2 weeks for any reason should generally result in discontinuation from the study, unless the patient has demonstrated a clinical benefit from therapy and would like to continue dosing with study drug after discussion between the investigator and the Sponsor.

Table 22: Recommended PLX9486 Dose Modifications (Including Stopping Rules)

All Drug-Related Toxicities	Frequency	When to Hold or Stop	When to Restart Dose ^a
Grade 3 or 4 neutropenia	1st Appearance	Interrupt until ANC recovers to $\geq 1 \times 10^9/L$; growth factor support permitted	If recovered to ANC $\geq 1 \times 10^9/L$ in ≤ 7 days, resume at same dose.
			If not recovered to ANC $\geq 1 \times 10^9/L$ after 7 days, reduce dose by 1 dose level.
		Interrupt until ANC recovers to $\geq 1 \times 10^9/L$; growth factor support permitted	If recovered to ANC $\geq 1 \times 10^9/L$ in ≤ 7 days, reduce dose by 1 dose level.
	2nd Appearance	Interrupt until ANC recovers to $\geq 1 \times 10^9/L$; growth factor support permitted	If recovered to ANC $\geq 1 \times 10^9/L$ in ≤ 7 days, reduce dose by 1 dose level.
			If not recovered to ANC $\geq 1 \times 10^9/L$ after 7 days, reduce dose by 2 dose levels.

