	2nd Appearance	Interrupt until resolved (Grade 0–1); start symptomatic treatment if possible	If recovered ≤ 5 days, reduce dose by 1 dose level.
			If symptoms persist for >5 days despite supportive management, discontinue permanently.
Other Grade 4 toxicities (excluding trans-aminase increases)	1st Appearance	Interrupt until resolved (Grade 0–1); start symptomatic treatment if possible	If recovered <5 days, reduce by 1 dose level.
			If symptoms persist for ≥ 5 days despite supportive management, discontinue permanently.
	2nd Appearance	Discontinue permanently; start symptomatic treatment if possible	N/A

All Drug-Related Toxicities	Frequency	When to Hold or Stop	When to Restart Dose ^a
Transaminase increases	
 ALT or AST $>8 \times$ ULN ALT or AST $>5 \times$ ULN for more than 2 weeks ALT or AST $>3 \times$ ULN and Total bilirubin $>2 \times$ ULN or INR >1.5 (in absence of anticoagulation) ALT or AST $>3 \times$ ULN with the appearance of fatigue, nausea, vomiting, right upper quadrant pain or tenderness, fever, rash, and/or eosinophilia ($>5\%$). 	
Immediately hold dose and discuss with Medical Monitor.
 
Institute close monitoring. Any decision to restart after transaminases return to baseline must be discussed with the Medical Monitor.
	N/A
QTcF >500 msec or 60 msec increase from baseline verified on repeat ECG	First appearance	
Interrupt study drug until resolved.
	
Upon recovery to QTc ≤ 500 ms (Grade ≤ 2), restart at a reduced dose (at least one dose level).
 
Permanently discontinue study drug if the QTc interval remains >500 ms and increased >60 ms from pretreatment values (after controlling cardiac risk factors for QT prolongation e.g., electrolyte abnormalities, congestive heart failure, and bradyarrhythmias)^b.

Note: The guidelines in this table apply to all parts of the study.

^a See [Section 9.2](#) for dose levels.

^b QTc: Only one dose reduction is permitted per patient. Prior to and following treatment initiation or after dose modification of study drugs for QTc prolongation, evaluate ECG and electrolytes (including potassium, magnesium, and calcium) after 15 days, and monthly thereafter or more often as clinically indicated.

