Reductions or interruptions of PLX3397 for toxicity may take place at any time during the study according to the guidelines in [Table 23](#), [Table 24](#), and [Table 25](#). Dose reduction/interruption guidelines for hematologic and nonhematologic treatment-related AEs are based on severity. Dose interruptions can be implemented at the discretion of the treating Investigator to manage intolerable or clinically significant toxicity. If a dose interruption is required, study assessments should be performed as scheduled, irrespective of the study drug delay, with the exception of PK

assessments, which should be deferred until treatment is resumed. Interruptions due to toxicity lasting >14 days require treatment discontinuation unless the medical monitor approves continuation.

Table 23: Recommended PLX3397 Dose Modifications (Including Stopping Rules and Excluding Transaminase Increases)

All Drug-Related Toxicities	Frequency	When to Hold or Stop	When to Restart Dose ^a
Grade 3 or 4 neutropenia	1st Appearance	Interrupt until ANC recovers to $\geq 1 \times 10^9/L$; growth factor support permitted	If recovered to ANC $\geq 1 \times 10^9/L$ in ≤ 7 days, resume at same dose.
			If not recovered to ANC $\geq 1 \times 10^9/L$ after 7 days, reduce dose by 1 dose level.
	2nd Appearance	Interrupt until ANC recovers to $\geq 1 \times 10^9/L$; growth factor support permitted	If recovered to ANC $\geq 1 \times 10^9/L$ in ≤ 7 days, reduce dose by 1 dose level.
			If not recovered to ANC $\geq 1 \times 10^9/L$ after 7 days, reduce dose by 2 dose levels.
Grade 3 or 4 febrile neutropenia	3rd Appearance	Interrupt until ANC recovers to $\geq 1 \times 10^9/L$; growth factor support permitted	If recovered to ANC $\geq 1 \times 10^9/L$ in ≤ 7 days, reduce dose by 1 dose level.
			If not recovered to ANC $\geq 1 \times 10^9/L$ after 7 days, discontinue permanently.
	4 th Appearance	Discontinue	
	1st Appearance	Interrupt until ANC and fever recover; provide growth factor support	If recovered to ANC $\geq 1 \times 10^9/L$ and T $\leq 38^{\circ}C$ in ≤ 7 days, reduce dose by 1 dose level.
			If not recovered to ANC $\geq 1 \times 10^9/L$ after 7 days, discontinue permanently.
Grade 3 or 4 thrombocytopenia without bleeding	2nd Appearance	Interrupt until ANC and fever recover; provide growth factor support	If recovered to ANC $\geq 1 \times 10^9/L$ and T $\leq 38^{\circ}C$, reduce dose by an additional 1 dose level.

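### The QTc row of Tables 22 and 23 holds dosing for a 60 msec rise from baseline but prints a restart value only for QTc above 500 msec

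*Protocol*

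**What the plan says.** Tables 22 and 23 in Section 9.4 carry the same QTc row.

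- **Trigger:** "QTcF >500 msec or 60 msec increase from baseline verified on repeat ECG".
- **Hold:** "Interrupt study drug until resolved". The row does not say what counts as resolved when the trigger was the rise.
- **Restart:** once QTc has come back to 500 ms or less, labelled Grade 2 or less, dosing resumes at least one dose level lower. No change-from-baseline value is given.
- **Permanent stop:** "Permanently discontinue study drug if the QTc interval remains >500 ms and increased >60 ms from pretreatment values", once cardiac risk factors have been controlled. Both parts are needed.
- **Footnote b:** for QTc, "Only one dose reduction is permitted per patient". ECG and electrolytes are checked after 15 days and then monthly, or more often if clinically indicated.

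Table 22 applies to all parts of the study. For the combination parts (2b and 2e), Section 9.4 adds that when one drug is held for an adverse event, "both drugs need to be discontinued until the adverse event resolves per the dose modification guidelines". Two general limits also apply: "Dosing interruptions longer than 2 weeks for any reason should generally result in discontinuation from the study", unless a patient who is benefiting continues by agreement, and, in the PLX3397 text, "Interruptions due to toxicity lasting >14 days require treatment discontinuation unless the medical monitor approves continuation".

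**The concern.** The hold has two alternative triggers, and recovery is defined for one of them. For a patient held only because QTcF rose by 60 msec, the hold column implies waiting until the event has gone, while the value in the restart column is already satisfied. The two columns therefore give different answers for the same ECG. Taken at its word, the restart column permits re-dosing at a lower level with the trigger still present.

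That matters in two ways. Because footnote b allows a single QTc reduction, restarting while the rise persists spends it. In Parts 2b and 2e the partner drug is tied to the same guidelines, so the gap also bears on when that drug resumes.

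**Working it through.** **Inputs.** Trigger, restart and permanent-stop values come from the QTc rows of Tables 22 and 23. The eligible range comes from Section 8.2, exclusion 6c: patients are excluded at a screening QTcF of 450 msec or more (males) or 470 msec or more (females). Write B for baseline and Q for on-treatment QTcF, in whole msec.

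**The printed rules**

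- Hold: Q > 500, or Q − B ≥ 60
- Restart at a reduced dose: Q ≤ 500
- Permanent stop: Q > 500 and Q − B > 60

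**Held for the rise alone.** This means B + 60 ≤ Q ≤ 500. Such values exist when B + 60 ≤ 500, that is, B ≤ 440. Every Q in that band meets the restart value, because Q ≤ 500 is part of what defines it. The band runs from B + 60 to 500, its width is 440 − B, and the largest rise inside it is 500 − B.

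| Baseline B | QTcF that triggers the hold and meets the restart value | Width, 440 − B | Rise from baseline |
|---|---|---|---|
| 380 | 440 to 500 | 60 | 60 to 120 |
| 400 | 460 to 500 | 40 | 60 to 100 |
| 420 | 480 to 500 | 20 | 60 to 80 |
| 440 | 500 only | 0 | 60 |

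All four baselines lie below both exclusion limits, so the case is reachable in men and women. From B = 441 upward, 441 + 60 = 501 already exceeds 500, so the printed restart value works there. If the trigger is read as a rise of more than 60, the bound moves by 1 msec: B + 61 ≤ 500 gives B ≤ 439.

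**Permanent stop.** It requires Q > 500, so no patient with a rise alone can meet it, however long the rise lasts.

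**Comparison with other rows of the same tables.** Where another event has two parts, recovery names both. Febrile neutropenia needs the neutrophil count and the temperature to recover. Thrombocytopenia with bleeding needs the platelet count to recover and the bleeding to stop. In Table 22, any restart after a transaminase hold is considered only once values are back at baseline. Only the QTc row uses a change from baseline as a trigger and then leaves it out at recovery.

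**The case against.** The best defence is the hold column. The row is headed by the event, and the hold lasts until that event resolves. On a plain reading, a patient held for the rise stays off drug until the rise has gone, and the restart wording simply fits patients who had exceeded 500. This is a fair reading and probably the intended one. But the row does not define resolution that way. The Grade 0–1 definition in other rows is not carried over, and the only recovery stated here is the absolute value. The conflict between the columns stands.

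The second defence is oversight. Section 9.4 makes reductions of either drug conditional on a decision by the sponsor's Medical Monitor, calls the parameters a guide, and wants all adjustments made in consultation. Since every QTc restart is a dose reduction, one sponsor role should see each case. This stands as a limit on the risk and on differences between sites, but it gives the Medical Monitor no value to apply.

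The synopsis, summarising 49 treated patients, mentions one DLT and one treatment-related SAE, both anemia, and no QTc event. It is not a full adverse event listing, but nothing in it suggests that the case is frequent.

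A reader might also infer that a patient with QTc above 500 and a rise of 60 ms or less is stuck on hold until the 2-week limit applies. The text does not support that: recovery to 500 ms or less is itself the exit, at a reduced dose.

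**Conclusion.** The point holds as an internal conflict in one row of two tables. For a hold triggered by the rise alone, possible at baselines of 440 ms or less, the printed restart value is met from the outset, with rises of up to 500 − B still present. The finding rests only on the printed thresholds, read in whole msec, and does not depend on which pre-dose ECG serves as baseline.

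A reader might infer that the protocol sends such patients straight back onto drug unsupervised. The documents do not support that: the hold instruction, the mandatory reduction and the Medical Monitor's decision all stand in between. Nor does the gap show that the permanent-stop rule has to be rewritten. The protocol gives no QTc event rate, so no frequency is claimed. The correction is worth making as a minor safety-rule change. Endpoints, sample size and analyses are untouched.

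**What to change.** In the restart column of the QTc row in both tables, require recovery to a QTc of 500 ms or less **and** an increase from baseline below 60 ms before restarting at a reduced dose. Leave the permanent-stop rule as it is, and leave the two interruption limits as they are, with their clinical-benefit and Medical Monitor exceptions. Those limits then govern a rise that does not go away.

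The added condition binds only where it is needed. At B = 441 or above, Q ≤ 500 already means a rise of at most 500 − 441 = 59. At B = 400, restart would need a QTc below 400 + 60 = 460.

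The cost is the wording of one cell in each of Tables 22 and 23. A few patients may be held longer, and some of those could reach the existing interruption limits. Flow charts do not change.
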